Specific exercises will be introduced in an orderly fashion across the pre-quit period. For instance, explicit exposure to interoceptive cues will begin later in the pre-quit period, after the participant has mastered techniques associated with exteroceptive cue exposure. However, the counselor will begin to address interoceptive cues earlier, while the participant is mastering exteroceptive cue exposure. In addition, participants will receive a rubber wristband (along with a spare) with a "Countdown" logo that will serve as an extinction retrieval cue, in order to improve the generalizability of extinction and reduce renewal to conditioned responding (Brooks & Bouton, 1994; Collins & Brandon 2002). Participants will be instructed to wear this wristband only while smoking during the last week of the pre-quit period, and to wear it continuously for up to one month after the target quit date (TQD). The worksheets will be collected at the end of the pre-quit period and scored to assess adherence to instructions (e.g., monitoring of smoking situations; extinction strategies used).

The bulk of the intervention will be provided via the self-help workbook, including advice for minimizing withdrawal and managing cravings after the TQD. In order to maximize treatment fidelity at this developmental stage, the workbook will be supported by brief in-person counseling provided at each VLNC cigarette distribution session. Counseling sessions will review the didactic information included in the workbook, including the extinction-facilitation strategies, exercises, and worksheets. Counselors will encourage participants to continue using the FE techniques throughout the pre-quit period, and highlight the importance of restricting all smoking during the treatment period to the study cigarettes provided. Counselors will also introduce techniques that are timed for different points during this period. For instance, as mentioned above, introduction of exposure to interoceptive cues will occur later in the pre-quit period, after the participant has mastered techniques associated with exteroceptive cue exposure. The TQD will be scheduled for one week after the fifth weekly session (+/- 3 days). Participants will receive brief counseling during a final session one week (+/- 3 days) after the TQD. Additional details regarding the content of the treatment sessions will be specified upon completion of the intervention development process.

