3) Practicality represents the broadest of the feasibility constructs. This will encompass the degree to which we are able to carry out all the elements of the planned developmental pilot study successfully and efficiently. This includes recruitment, screening, randomization, and treatment components. For these elements of the study, we will record number of attempts, duration, protocol deviations and errors, and suggestions for improvement.

Study 2. Randomized Controlled Trial (Aim 2), Intermediate Outcomes (Aim 3), and Mechanisms (Aim 4)

Study Goals and Overview. The primary goals of Study 2 are to test effects of the targeted intervention developed in Study 1 on smoking cessation (Aim 2) and intermediate outcomes (Aim 3), as well as to explore potential mechanisms that could guide future implantation of this treatment strategy (Aim 4). Approximately 300 treatment-seeking smokers will be screened using similar methods and inclusion/exclusion criteria as in Study 1. The expectation is that 80% of participants (n=208) will be eligible and randomized to one of four conditions (52 per condition) over a 3 year period. The four conditions will comprise a 2 x 2 between-subjects design, with facilitated extinction (targeted) treatment (present vs. absent) crossed with tapering schedule (immediate vs. gradual). As in Study 1, once a participant has been deemed eligible, a baseline week of smoking NNC study cigarettes will be followed by four weeks of smoking VLNC cigarettes, either through immediate or gradual reduction to the lowest level. Five weekly counseling sessions will occur (at the start of each week), and the Target Quit Date will occur one week after the fifth weekly session (+/- 3 days). On the Target Quit Date, participants will attend an additional session, including counseling as well as two tests of intermediate outcomes (cue reactivity and cigarette purchase task). Follow-up visits will occur at 2 and 6 months following the TQD (+/- 7 days). Please see Appendices on pages 33-34 for further details.

Exclusion Criteria: Study 2 exclusion criteria will match those of Study 1, with the following modifications: (a) use of smoking cessation medications will be exclusionary only for the past month and with the exception of sporadic use of NRT for non-cessation purposes, (b) use of

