Intervention Phase. As in Study 1, all participants will be given a supply of normal nicotine content (NNC; .8 mg yield) study cigarettes to smoke for a baseline week, based on typical # cigarettes/day x 1.5. However, if a participant normally smokes 120mm cigarettes, then the amount supplied will be determined by multiplying their typical number of cigarettes/day x 2 (because the Spectrum cigarettes are regular length at approximately 80mm). This will introduce participants to the taste and feel of Spectrum research cigarettes, prior to receiving reduced nicotine cigarettes, thereby avoiding the confounding of changing brand and nicotine content simultaneously. Prior to the baseline session, participants will be randomly assigned to one of four treatment conditions, that vary according to a 2 x 2 between subject design: (1) targeted intervention with immediate transition to VLNC cigarettes, (2) targeted intervention with gradual transition to VLNC cigarettes, (3) standard intervention with immediate transition to VLNC cigarettes, (4) standard intervention with gradual transition to VLNC cigarettes. Overall, the intervention phase will consist of six visits, with five of them preceding the TQD which will occur one week after the fifth weekly session. The sixth session will occur on the TQD. At each of the pre-quit visits, participants will (1) receive their supply of study cigarettes for the upcoming week, (2) complete assessments related to compliance and reactions to assigned study cigarettes, (3) answer questions regarding health changes (if any) and date/length of last menstrual period for pre-menopausal women (to assess potential pregnancy), which will be documented on the 'Health Changes Questionnaire' (4) complete a Cigarette Purchase Task for their study and usual brand cigarettes (5) complete the QSU-brief for study and usual brand cigarettes (6) complete a Cigarette Evaluation Scale for the study cigarettes (7) complete the Drug Effects/Liking Scale for their study cigarettes (8) complete the Timeline-Follow Back interview to update their smoking, alcohol, and drug use since the prior visit, and (9) receive brief counseling according to condition. As in Study 1, if the participant's breath alcohol level is > 0.03 the researcher will not start the session.

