Based on participant and counselor feedback from Study 1, the FE workbook was converted to a series of weekly booklets. The content is similar to what was included in the pilot study, but the workbook series now includes additional cessation-related advice and enhanced graphics. The targeted intervention will consist of the FE workbook series and supportive counseling (as developed and refined in Study 1), whereas the standard intervention will consist of the "Clearing the Air" booklet (National Cancer Institute; NIH Publication No. 11-1647), along

with a brief study introduction booklet which will explain the rationale for using reduced nicotine cigarettes as a cessation aid. Additionally, the standard intervention will entail an equal duration (relative to targeted intervention) of cognitive-behavioral smoking cessation counseling that follow recommendations from the USPHS Clinical Practice Guidelines along with supplemental handouts (Fiore et al., 2008). Counseling sessions for all conditions will include discussion of compliance with smoking only study cigarettes, as well as other study procedures. Although all participants will be strongly encouraged to smoke only study cigarettes, they will be told there is not a penalty for use of non-study cigarettes, and that it is crucial for them to report any use of non-study cigarettes or other nicotine or tobacco products. The VLNC immediate and gradual tapering conditions will be as described above, with participants, counselors and experimenters blind as to condition assignment.

Target Quit Date Participants will attend a session on their Target Quit Date. During this visit, all study cigarettes distributed during their prior visit will be collected, additional cessation counseling will be provided, physiological measures (i.e., carbon monoxide, breath alcohol, blood pressure, and heart rate) will be collected, and possible health changes will be assessed. Participants will also complete a Cigarette Evaluation Scale for their study cigarettes, the QSU for their study and usual brand cigarettes, the Drug Effects/Liking Scale for their study cigarettes to obtain intermediate smoking-related outcomes: cue-reactivity and cigarette purchase task (see descriptions below). Lastly, those randomized to the targeted intervention will be provided with the final Countdown booklet.

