intensity (consumption at zero price), Omax (maximum amount of money allocated to cigarettes), breakpoint (the first price at which a participant reports zero consumption) and Pmax (the price at which Omax occurs). This task will indicate whether prolonged VLNC use reduces cigarette demand and increases sensitivity to increases in cigarette costs.

Smoking Cessation Outcomes:

- 1) Daily Abstinence Assessments. Daily abstinence for each of the first seven days of the quit attempt will be assessed through participant self-report. Depending on participant preference, they may be contacted through text, telephone, and/or e-mail. If contacted through email or text, participants will be prompted to a study survey link, where they will complete the brief assessment online.

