- 2) Follow-up Assessments. Participants will attend follow-up sessions at 2 and 6 months following the TQD (+/- 7 days). Smoking status using established self-report and biochemical indices will be measured. As in Study 1, we will continue to obtain indices of feasibility and acceptability (see above) to inform and support future clinical trials and mechanistic studies to understand the effects of VLNC cigarettes for smoking cessation. At these sessions the participants will be asked about possible health changes, complete a drug use questionnaire, a Cigarette Purchase Task, the QSU for their study and usual brand cigarettes, and complete the Timeline-Follow Back interview. In addition, a brief questionnaire (the 2 and 6-month follow-up form) will capture their stage in the quitting process, use of additional cessation products/methods (if any), and wristband use for those randomized to the targeted intervention. Participants will be compensated (\$30) for each follow-up session attended. If a participant is unable or unwilling to attend either of these follow-up visits in-person, we will attempt to obtain these data over the telephone. If participants conduct these follow-ups via the telephone, they will be provided a compensation of \$30 (gift card) through the mail. If participants are unable to complete the follow-ups via the telephone or in-person, they will be mailed the 2 and 6-month follow-up questionnaire, accordingly. If a participant completes the 2 or 6-month follow-up questionnaire via the mail, they will receive a \$20 gift card. If a participant is lost to follow-up after at least 5 contact attempts have been made, a certified letter will be mailed with a scheduled appointment time and a request to return investigational study product.

Retention: We will provide study participants with small items (e.g., notepads, pens, water bottles) upon completion of each visit (following the baseline session), to improve retention. In addition, a letter will be sent to participants reminding them of their upcoming 2 and 6-month follow-up visits accordingly. If study staff are unable to locate participants during the treatment or follow-up phase, third-party directory services may be utilized in order to reach them (i.e., whitepages.com).

Study Debriefing: After data collection from all participants is complete, participants will be mailed a letter informing them of their condition assignment (and preliminary findings, if available).

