Sources of Materials: Data collected for research purposes only include: (1) biological specimens, including carbon monoxide (CO) and alcohol breath tests (to verify smoking status and abstinence compliance), and a urine specimen (for drug, cotinine and pregnancy testing); (2) interview and self-report measures (e.g., demographic, medical, psychological, smoking behavior, treatment satisfaction and compliance); and (3) self-reported outcomes during cue reactivity and cigarette purchase tasks.

Potential Risks: Potential risks include loss of confidentiality or discomfort while completing interview or questionnaire assessments. The measures to be used are generally benign, and protection of confidentiality is a high priority within our lab (see below). In addition, participants may experience elevated nicotine withdrawal and/or cravings during pre-quit smoking of very low nicotine content (VLNC) cigarettes or during a smoking cessation attempt. Nicotine withdrawal symptoms include: irritability, frustration, or anger; anxiety; difficulty concentrating; increased appetite; restlessness; depressed mood; and insomnia. Nicotine withdrawal symptoms are uncomfortable but of minimal risk. Finally, the research cigarettes have been previously tested and found to be safe, with side effects that are similar to usual brand cigarettes. In prior studies, compensatory smoking was minimal and transient, and higher levels of toxicant exposure was generally not observed. Nonetheless, compensatory smoking may occur and lead to increased levels of toxicant exposure.

Avoiding Risks to Fetus:

If participants choose to be sexually active, they should use an appropriate "double barrier" method of birth control (such as female use of a diaphragm, intrauterine device (IUD), or contraceptive sponge, in addition to male use of a condom) or the female should be using prescribed "birth control" pills, injections or implants. Female participants with child-bearing potential will be tested for pregnancy at the baseline session, the third weekly visit, and on the Target Quit Date session. If a participant becomes pregnant during the study she will be withdrawn from the study. Approximately 30 days after being withdrawn, the research staff will contact the participant to confirm her due date. The licensed medical professional will follow-up with the participant after delivery to ask questions about the baby's health.

Adequacy of Protection Against Risk

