Collection and Reporting of AEs and SAEs. At each study visit, participants will be asked to report any negative health changes on the 'Health Changes Questionnaire' since the prior visit. Any negative changes will be recorded on an Adverse Event (AE) form. This form will include fields for describing the adverse event, as well as the onset, duration, status (completed vs. ongoing), and any steps taken to resolve the AE. The form will be reviewed by the study physician (or by the study investigators during the follow-up phase) prior to the next study visit, and the AE will be monitored until it is marked as resolved. All AEs will be assessed to determine if they meet criteria for an SAE. Monitoring by the PI will be conducted on an ongoing basis and monitoring by the IRB is conducted at the continuing reviews as scheduled by the IRB and upon receiving reports of AEs from the PI.

Management of SAEs and Other Study Risks. Serious adverse events (SAEs), as defined by the FDA, will be systematically evaluated at each study visit. All product-related adverse events of a non-serious nature will be reported to the IRB at the time of annual renewal. Any SAE, whether or not related to study product or participation, will be reported to the IRB, the study sponsor (State of Florida Department of Health), and the FDA. A participant may be discontinued from the study or withheld from study product if the study physician (or his designee) determines it is the best course of action in order to protect the safety of the participant. In the event that a participant either withdraws from the study or the investigator or study physician(or licensed medical professional designated to consult in his absence) decides to discontinue a participant due to an SAE, the participant will have appropriate follow-up medical monitoring. The participant experiencing a SAE will be followed until the problem resolved, stabilizes, or is clearly unrelated to the study cigarettes. Outcome of SAEs will be periodically reported and a summary of SAEs will be provided in study progress reports to the IRB, sponsor, and FDA.

Stopping Rules. For the participant's protection, participants will be withdrawn immediately from the study if any of the following occur:

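### In Study 2 no scheduled health question is described between the quit-date visit and the 2-month follow-up, and none is described for participants followed only by mail

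*Combined protocol and SAP*

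**What the plan says.** **Visit schedule.** The Study 2 Intervention Phase section ends treatment visits on the target quit date (TQD): "The sixth session will occur on the TQD". At that visit "possible health changes will be assessed" (Target Quit Date section). The Study 2 overview gives the next visits: "Follow-up visits will occur at 2 and 6 months following the TQD (+/- 7 days".

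**Safety questions.** Collection and Reporting of AEs and SAEs (Section E) ties active questioning to visits: "At each study visit, participants will be asked to report any negative health changes on the 'Health Changes Questionnaire' since the prior visit". The next section ties the evaluation of serious adverse events (SAEs) to visits as well. The Appendix table of procedures marks the Health Changes Questionnaire and the AE form at Visits 2 to 6 and at 2 and 6 months.

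**Contacts in between.** Under Smoking Cessation Outcomes, item 1: "Daily abstinence for each of the first seven days of the quit attempt will be assessed through participant self-report". These contacts are by text, telephone or e-mail. No health item is described, and they have no row in the Appendix table.

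**Mail route.** Follow-up Assessments asks about health changes at attended sessions and seeks the same data by telephone. Failing both: "If participants are unable to complete the follow-ups via the telephone or in-person, they will be mailed the 2 and 6-month follow-up questionnaire, accordingly". That form is described as covering quitting stage, other cessation products or methods, and wristband use.

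**Stated risk.** Potential Risks (Section E) says that "participants may experience elevated nicotine withdrawal and/or cravings during pre-quit smoking of very low nicotine content (VLNC) cigarettes or during a smoking cessation attempt".

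**The concern.** The plan names the quit attempt as a time when withdrawal may be elevated, and it lists depressed mood, anxiety and insomnia among the symptoms. Yet the schedule describes no occasion to ask about health in the weeks just after quitting. Under Protection Against Risk, the Prime MD is triggered by what a participant endorses at a visit, so it too has no scheduled occasion in that window. The Stopping Rules provide for withdrawal after a suicide attempt or psychiatric hospitalization at any time during participation, which requires that the event become known.

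Study 1 differed. It had a session soon after quitting: "Participants will receive brief counseling during a final session one week (+/- 3 days) after the TQD". Under the general rule in Section E, that session would carry a health question. The Study 2 schedule has no counterpart.

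What is at stake is the timing and completeness of AE and SAE ascertainment after the quit date. The quality of the AE summary promised in the Data and Safety Monitoring Plan depends on it.

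**Working it through.** This is mainly a comparison of schedule and forms, with simple date arithmetic.

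**1. Is there an unlisted session in the gap?** The note to Table 2 (Project Timeline) gives the expected session counts:
- 208 + 198 + 188 + 178 + 168 + 158 + 148 + 138 = 1,384, as stated.
- 1,384 / 42 months = 33.0 per month, as stated.

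The list goes straight from 158 quit-date sessions to 148 at 2 months. The counts add up with no session in between.

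**2. Length of the gap.** The plan does not give 2 months in days, so I assume 60 to 61.
- Shortest: 60 − 7 = 53 days.
- Longest: 61 + 7 = 68 days.

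**3. Gap left after the first-week contacts.** Subtract 7 days: 53 − 7 = 46 and 68 − 7 = 61 days.

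**4. Contacts already planned in the gap.** 7 × 158 = 1,106. This is a ceiling: it assumes that everyone expected at the quit date responds every day, and it includes self-completed online surveys.

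**5. Safety questions by route, as described:**

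| Occasion | Health question described? |
|---|---|
| Visits 2 to 6 (Visit 6 = TQD) | Yes |
| Daily contacts, days 1 to 7 | No; abstinence only |
| Day 8 to 2-month follow-up | No contact scheduled |
| 2 and 6 months, attended | Yes |
| 2 and 6 months, telephone | Yes; same data sought |
| 2 and 6 months, mail | No; follow-up questionnaire only |

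The Appendix lists the Health Changes Questionnaire and the 2- and 6-month questionnaires as separate forms. Mailing one therefore does not imply mailing the other.

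**6. How many are followed by mail?** The documents do not say. Of the 158 expected at the quit date, 158 − 148 = 10 (6.3%) are not expected at 2 months and 158 − 138 = 20 (12.7%) are not expected at 6 months. These are falls in expected session counts, not counts of mail responders.

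**The case against.** The case on the other side has real substance.

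- **Safety monitoring does not stop at the quit date.** A reader might infer that it does. Protection Against Risk has participants call the investigator, counselor or study physician about excessive side effects, including after the TQD. AEs already open are monitored until resolved. The gap concerns only scheduled questions about new events.
- **Events in the gap are not shown to be lost.** A reader might infer that they are missed and that reported risk is understated. The Health Changes Questionnaire looks back to the prior visit, so an attended or telephoned 2-month follow-up covers the whole interval, though by recall. Someone who replies by mail at 2 months may still be asked at 6 months. Nothing shows that mail responders are sicker than others.
- **The forms are not in the documents.** A reader might infer that the daily survey and mailed questionnaire contain no health item. The text supports only that none is described. Aim 4 plans to analyze withdrawal after the TQD, so some post-quit measurement is envisaged. The Appendix also marks the Health Changes Questionnaire at 2 and 6 months without distinguishing the mode of follow-up.
- **The plan rates the risk as low.** Potential Risks calls withdrawal uncomfortable but of minimal risk, study cigarettes are collected on the quit date, and unstable psychiatric disorders are excluded at entry. Nor does post-quit withdrawal fall wholly outside the weekly visits: by the quit date participants have smoked the lowest-nicotine cigarettes for one week (gradual) or four (immediate).
- **Asking in week 1 does not close the gap.** About 46 to 61 days remain.

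These points rule out a claim of lost events or of demonstrated harm. They leave the schedule facts untouched: contact is already being made in the first quit week and by mail, and the text describes no health question on either occasion.

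**Conclusion.** The point holds as an inexpensive improvement in AE and SAE ascertainment. As described, Study 2 has no scheduled health-change question for about 53 to 68 days after the quit date, and none for participants followed only by mail at that time point. The first figure rests on taking 2 months as 60 to 61 days. Both statements rest on the described content of forms that are not in the documents; if the daily survey or the mailed form already carries a health item, the protocol need only say so. The size of the mail group is unknown, so the amount of AE data affected cannot be estimated.

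**What to change.** - **First quit week.** Add the health-change item from the existing Health Changes Questionnaire to the daily contacts, at minimum on day 7.
- **Mail follow-up.** Enclose the existing Health Changes Questionnaire with the mailed 2- and 6-month forms.
- **Recording.** Enter replies on the AE form under the existing process in Collection and Reporting of AEs and SAEs. How and when a positive reply is acted on stays with the sponsor's existing procedures; no new clinical trigger is proposed here.
- **Text.** Reconcile Daily Abstinence Assessments, Follow-up Assessments, Protection Against Risk, Collection and Reporting of AEs and SAEs, and the Appendix table, so that each states when, and by which mode of contact, health changes are asked about.

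**Cost.** Protocol and survey wording, one more item on contacts already planned, and one more sheet in an existing mailing. The Appendix already allows remote administration of this questionnaire for COVID-19. Staff must review more replies, including self-completed online ones, and each contact is slightly longer, equally in all four arms. The change does not cover the 46 to 61 days after day 7, which would still depend on call-in and on recall at 2 months.
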